7.2 Serious adverse event reporting

To ensure patient safety, every SAE, regardless of causality, occurring after the patient has provided informed consent and until 30 days after the last study visit must be reported to Novartis within 24 hours of learning of its occurrence.

Any SAEs experienced after the 30 days period should only be reported to Novartis if the investigator suspects a causal relationship to study treatment.

Recurrent episodes, complications, or progression of the initial SAE must be reported as follow-up to the original episode, regardless of when the event occurs. This report must be submitted within 24 hours of the investigator receiving the follow-up information. An SAE that is considered completely unrelated to a previously reported one should be reported separately as a new event.

Information about all SAEs is collected and recorded on the paper Serious Adverse Event Report Form. The investigator must assess the relationship to study drug, complete the SAE Report Form in English, and send the completed, signed form by fax within 24 hours to the local Novartis Drug Safety and Epidemiology Department. The telephone and telefax number of the contact persons in the local department of Novartis Drug Safety are listed in the investigator folder provided to each site and is also listed below. The original copy of the SAE Report Form and the fax confirmation sheet must be kept with the case report form documentation at the study site. Follow-up information should be provided using a new paper SAE Report Form stating that this is a follow-up to a previously reported SAE and sent by giving the original report date.

Follow-up information provided should describe whether the event has resolved or continues, if and how it was treated, whether the treatment code was broken or not and whether the patient continued or withdrew from study participation. Each re-occurrence, complication, or progression of the original event should be reported as a follow-up to that event regardless of when it occurs.

If the SAE is not previously documented in the Investigator's Brochure or Package Insert (new occurrence) and is thought to be related to the Novartis study drug, a Novartis Drug Safety and Epidemiology Department associate may urgently require further information from the investigator for Health Authority reporting. Novartis may need to issue an Investigator Notification (IN) to inform all investigators involved in any study with the same drug that this SAE has been reported.

SAE Reporting to Ministry of Health and Ethical Committee

Local Novartis Turkey Drug Safety Department will report all suspected unexpected serious adverse reactions (SUSARs) to Ministry of Health as per The Regulation on Clinical Trials and Guidance on the collection, verification and submission of Adverse Event/Reaction Reports Occurring During Clinical Trials of Medicinal Products and Biological Products.

7.3 Pregnancy reporting

To ensure patient safety, each pregnancy occurring while the patient is on study treatment must be reported to Novartis within 24 hours of learning of its occurrence. The pregnancy should be followed up to determine outcome, including spontaneous or voluntary termination, details of the birth, and the presence or absence of any birth defects, congenital abnormalities, or maternal and/or newborn complications.

Pregnancy should be recorded on a Clinical Trial Pregnancy Form and reported by the investigator to the local Novartis Drug Safety and Epidemiology Department. Pregnancy follow-up should be recorded on the same form and should include an assessment of the possible relationship to the study treatment.

Any SAE experienced during pregnancy must be reported on the SAE Report Form.

Pregnancy outcomes must be collected for the female partners of any males who took study treatment in this study. Consent to report information regarding these pregnancy outcomes should be obtained from the female partner.

Contact information for Novartis Drug Safety department:

Tel: [REDACTED]

Novartis Drug Safety Fax: [REDACTED]

Novartis Drug Safety Mailbox: [REDACTED]

8 Data review and database management

8.1 Site monitoring

Before study initiation, at a site initiation visit or at an investigator's meeting, a Novartis representative will review the protocol and CRFs with the investigators and their staff. During the study, the field monitor will visit the site regularly to check the completeness of patient records, the accuracy of entries on the CRFs, the adherence to the protocol and to Good Clinical Practice, the progress of enrollment, and to ensure that study treatment is being

stored, dispensed, and accounted for according to specifications. Key study personnel must be available to assist the field monitor during these visits.

The investigator must maintain source documents for each patient in the study, consisting of case and visit notes (hospital or clinic medical records) containing demographic and medical information, laboratory data, electrocardiograms, and the results of any other tests or assessments. All information on CRFs must be traceable to these source documents in the patient's file. *Data not requiring a separate written record will be defined before study start and will be recorded directly on the CRFs.* The investigator must also keep the original informed consent form signed by the patient (a signed copy is given to the patient).

The investigator must give the monitor access to all relevant source documents to confirm their consistency with the CRF entries. Novartis monitoring standards require full verification for the presence of informed consent, adherence to the inclusion/exclusion criteria, documentation of SAEs, and of data that will be used for all primary variables. Additional checks of the consistency of the source data with the CRFs are performed according to the study-specific monitoring plan. No information in source documents about the identity of the patients will be disclosed.

8.2 Data collection

Designated investigator staff must enter the information required by the protocol onto the Novartis CRFs that are printed on 3-part, non-carbon-required paper. Field monitors will review the CRFs for completeness and accuracy and instruct site personnel to make any required corrections or additions. The CRFs are forwarded to the Medical Documents Reception Center of Novartis or *CRO working on behalf of Novartis* by field monitors or by the investigational site, with one copy being retained at the investigational site. Once the CRFs are received by *Novartis or CRO working on behalf of Novartis*, their receipt is recorded, the original copy is placed in Central Files, and the non-carbon-required copy is forwarded to the responsible Data Management staff for processing.

8.3 Database management and quality control

Data from the CRFs are entered into the study database by Contract Research Organization (CRO) staff following their own internal standard operating procedures that have been reviewed and approved by Novartis.

Subsequently, the entered data are systematically checked by Data Management staff, using error messages printed from validation programs and database listings. Other errors or omissions are entered on Data Query Forms, which are returned to the investigational site for resolution. The signed original and resolved Data Query Forms are kept with the CRFs at the investigator site, and a copy is sent to Novartis so the resolutions can be entered into the database. Quality control audits of all key safety and efficacy data in the database are made prior to locking the database.

Concomitant medications entered into the database will be coded using the WHO Drug Reference List, which employs the Anatomical Therapeutic Chemical classification system. Concomitant procedures, non-drug therapies and adverse events will be coded using the Medical dictionary for regulatory activities (MedDRA) terminology.

8.4 Data Monitoring Committee

Not required.

8.5 Adjudication Committee

Not required.

9 Data analysis

9.1 Analysis sets

The Safety population will consist of all patients who received at least one intravitreal injection of ranibizumab.

All analyses will be performed using the Safety population

9.2 Patient demographics and other baseline characteristics

Descriptive statistics for continuous variables (i.e.: N, mean, standard deviation, median, maximum and minimum) and frequency and percent ranges for categorical variables will be given. Demographic data of the patients (including height and weight) and baseline visual acuity will be submitted as summary tables. Medical history and ocular medical history will be summarized per treatment arms.

9.3 Treatments

Descriptive statistics will be given for application of the study medication. To evaluate the dosage compliance, the percent range of the patient that accepted fully complied will be given. Concomitant medication/significant non-drug treatments will be summarized as numbers and per cents.

9.4 Analysis of the primary and key secondary variable(s)

9.4.1 Variable(s)

Mean change in Best-corrected visual acuity (BCVA) with ETDRS-like chart at a starting distance of 4 meters, at 12th month from baseline

9.4.2 Statistical model, hypothesis, and method of analysis

There is no special hypothesis intended for this study.

9.4.3 Handling of missing values/censoring/discontinuations

Close monitoring of the study sites will be planned to prevent any missing data and any early drop outs due to lost to follow up of the patients.

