5.2 Treatment arms

Patients will be assigned to one of the following “2” treatment arms randomly

A study-specific randomization scheme will be prepared by the CRO to follow up the randomization.

- Arm 1 - Labeled regime arm: Treatment will be given monthly and continued until maximum visual acuity is achieved (the patient’s visual acuity is stable for three consecutive monthly assessments performed while on ranibizumab treatment). Thereafter patients should be monitored monthly for visual acuity.

Treatment is resumed when monitoring indicates loss of visual acuity due to DME. Monthly injections should then be administered until stable visual acuity is reached again for three consecutive monthly assessments (implying a minimum of two injections). The interval between two doses should not be shorter than 1 month.

- Arm 2 - Wait and Extend regime arm: Lucentis (ranibizumab) 0.5 mg will be injected subsequently at baseline, month 1 and 2. After the three initial loading doses, patients will be called for control 1 month later. If the visual acuity has reached a stable level and there is no sign of edema on OCT, patients will not receive intravitreal injection and will be called to come back 6 weeks later. The interval is increased by 2 weeks until a maximum of 8 weeks as long as the patient presents as stable regarding visual acuity, central retinal thickness and clinical findings. If there is a negative change, the interval is shortened back to 4 weeks.

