5.5.10 Study completion and post-study treatment

The patient will be accepted to complete the study on Month 12 and in visit 14 for Labelled Regime Arm, the visit number may vary according the response of the patient for Wait and Extend Arm.

The investigator must provide follow-up medical care for all patients who are prematurely withdrawn from the study, or must refer them for appropriate ongoing care.

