5.5.11 Early study termination

The study can be terminated at any time for any reason by Novartis. Should this be necessary, the patient should be seen as soon as possible and treated for a prematurely withdrawn patient. The investigator may be informed of additional procedures to be followed in order to ensure that adequate consideration is given to the protection of the patient's interests. The investigator will be responsible for informing HA and/or ECs of the early termination of the trial.

6 Visit schedule and assessments

In the below table, all the required study assessments are shown and the visits for those assessments are shown with an "X" sign. The patients must be seen during their planned visit days with a ± 7 days visit window.

At a minimum, patients will be contacted for safety evaluations during the 30 days following the last study visit or following the last administration of ranibizumab, including a final contact at the 30-day point. Documentation of attempts to contact the patient should be recorded in the source documentation.

Assessment /Procedure	Phase	Screening		Main Treatment Visits / Control Visits												
	Visit for Labeled Regime Arm *	1	2	3	4	5	6	7	8	9	10	11	12	13	14	
	Visit for Wait and Extend Arm*	1	2	3	4	5	The visit numbers may vary according to the response of the patient.									
	Month	0		1	2	3	4	5	5	7	8	9	10	11	12	
Day	-7 to -1	B (1)	30	60	90	120	150	180	210	240	270	300	330	360	EoT	
Informed consent	X															
Incl/Exclusion criteria	X	X														
Randomisation		X														
Medical history	X															
Vital signs ^a	X	X	X	X	X	X	X	X	X	X	X	X	X	X	X	
Lab. Parameters (HbA1c and blood glucose)	X	X	X	X	X	X	X	X	X	X	X	X	X	X	X	
Renal Function Parameters (Urea, Creatinin, Albumin, Total Protein, Uric Acid)	X					X									X	
Pregnancy test ^b	X															
ECG (12-lead)	X														X	
Concomitant Medication	X	X	X	X	X	X	X	X	X	X	X	X	X	X	X	
Adverse events		X	X	X	X	X	X	X	X	X	X	X	X	X	X	
Treatment (injections) ^c		X	X	X	X ^d	X ^d	X ^d	X ^d	X ^d	X ^d	X ^d	X ^d	X ^d	X ^d		
Rescue Laser Treatment					X ^e	X ^e	X ^e	X ^e	X ^e	X ^e	X ^e	X ^e	X ^e	X ^e		
BCVA	X	X	X	X	X	X	X	X	X	X	X	X	X	X	X	
Ophthalmologic examination ^e	X	X	X	X	X	X	X	X	X	X	X	X	X	X	X	
Fundus photography	X														X	
FFA	X		X ^g	X ^g	X ^g	X ^g	X ^g	X ^g	X ^g	X ^g	X ^g	X ^g	X ^g	X ^g	X	
OCT	X		X	X	X	X	X	X	X	X	X	X	X	X	X	
Tonometry ^f	X	X	X	X	X	X	X	X	X	X	X	X	X	X	X	
VFQ-25	X ⁱ	X ⁱ													X	
Study Completion															X	

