6.2 Baseline characteristics

The below information will be recorded during screening/ visit 1

- Ocular medical history: primary diagnosis and all other ocular conditions

In addition below data will be collected during Screening/Visit 1 and Baseline/Visit 2 but if all the assessments/examinations are performed during Screening/Visit 1, they should not be repeated in Baseline/Visit 2. In this case, only the VFQ-25 and injection data should be completed in the CRF:

- Related medical history: significant medical conditions and surgeries start dates and current situation.
- Concomitant medication/significant non drug treatments: all applied medication/treatments

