9.4.4 Supportive analyses

Not applicable.

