6.14 EFFICACY EVALUATION

6.14.1 Visual Acuity

In order to demonstrate that the “wait and extend” regimen of ranibizumab is non-inferior to the posology described in the prescribing information, mean change in BCVA at month 12 from the baseline visit will be determined for both treatment groups, and a comparison will be made between the two groups using the Mann Whitney u test.

The number of patients with improvement in BCVA from baseline will be compared for the two treatment groups using the Chi-Square test (with Fisher’s Exact Test where appropriate).

The number of patients with improvement of 5 or more letters from baseline will be compared for the two treatment groups using the Chi-Square test (with Fisher’s Exact Test where appropriate).

The number of patients with improvement of 10 or more letters from baseline will be compared for the two treatment groups using the Chi-Square test (with Fisher's Exact Test where appropriate).

The number of patients with improvement of 15 or more letters from baseline will be compared for the two treatment groups using the Chi-Square test (with Fisher's Exact Test where appropriate).

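### No rule covers a missing Month-12 BCVA, so the non-inferiority comparison defaults to patients who have one and can be biased in either direction

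*Protocol*

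**What the plan says.** Protocol 9.4.3, headed as the section on missing values, censoring and discontinuations, states: "Close monitoring of the study sites will be planned to prevent any missing data and any early drop outs". It gives nothing further. Protocol 9.4.4 answers supportive analyses with "Not applicable". Protocol 9.1 states: "All analyses will be performed using the Safety population". That population is defined by at least one injection.

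SAP 6.14.1 gives the primary comparison: "mean change in BCVA at month 12 from the baseline visit will be determined for both treatment groups", followed by a Mann-Whitney test between arms. It has no rule for a missing value.

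Both documents expect loss. Protocol 9.7 and SAP 5.1 assume 20% drop-out over one year and respond by raising the sample from 86 to 104.

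On timing, Protocol 5.5.10 places completion at Month 12, which is Visit 14 in the labelled arm, while "the visit number may vary according the response of the patient for Wait and Extend Arm". Protocol 6 adds: "The patients must be seen during their planned visit days with a ± 7 days visit window". For wait-and-extend, Protocol 5.2 lengthens the interval in stable patients to at most 8 weeks, and "If there is a negative change, the interval is shortened back to 4 weeks". The visit table in Protocol 6 schedules BCVA at every visit.

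**The concern.** A rank test on Month-12 change can use only patients who have that change. With no rule for the others, the analysis becomes a Month-12 completer analysis, or a rule is chosen after open-label data have been seen.

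Enrolling more patients restores precision but does not remove bias. The trial is open-label and the arms follow different visit schedules, so the reasons for leaving may differ by arm. If poor responders leave wait-and-extend while labelled-arm loss is random, completers hide part of a real deficit. In the reverse case they show a deficit that does not exist. Equal numbers can be lost in both situations, so the attendance table planned in SAP 6 need not reveal either one. Nothing in the plan uses the earlier BCVA or tests how far the conclusion depends on the missing values.

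**Working it through.** **1. The plan's own sample size.** Inputs from Protocol 9.7: margin 5, SD 7, one-sided alpha 0.025, power 90%. A true difference of 0 is assumed, because none is stated. n per arm = 2 × (1.960 + 1.282)² × 7² / 5² = 41.2, so 42. By noncentral t, power is 89.9% at 42 and 90.6% at 43, so the stated 43 per arm reproduces. The inflation is 86 × 1.2 = 103.2, rounded to 104 (52 per arm). With 20% lost, 52 × 0.8 = 41.6 per arm remain, and power is still about 90% if there is no bias. The 20% allowance therefore deals with precision only.

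**2. Bias of a completer difference.** In each arm, the completer mean minus the full-arm mean is d × gap, where d is the fraction lost and gap is the completer mean minus the lost-patient mean. For the difference between arms:

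bias = d_W × gap_W − d_L × gap_L (W = wait-and-extend, L = labelled).

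With equal loss d this is d × (gap_W − gap_L). It is zero only if the gaps are equal, so equal numbers lost give no protection.

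**3. Illustration.** The documents give only the 20%. Everything else here is assumed: 52 per arm, 10 lost per arm, SD 7, Month-6 to Month-12 correlation ρ from 0.3 to 0.85, loss drawn from the worst 40% at Month 6 in one arm and random in the other. The mean of the lowest 40% of a standard normal is −0.966. So

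bias = (10/42) × 0.966 × 7 × ρ = 1.61ρ, that is 0.48 letters at ρ = 0.3 and 1.37 at ρ = 0.85.

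This needs no decision rule. For error rates I read non-inferiority as a lower 95% limit above −5; that rule is mine, since the SAP's test has no margin. SE = 7 × √(2/42) = 1.53.

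- True deficit 5, selective wait-and-extend loss: false non-inferiority = 1 − Φ(1.96 − bias/SE) = 5.0% to 14.4%.
- True difference 0, selective labelled loss: power = Φ((5 − bias)/SE − 1.96) = 84% to 66%.

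Simulation with t intervals (8,000 replicates per cell) agrees:

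| ρ | Completer estimate at true −5 | False non-inferiority | Power at true 0, labelled loss selective |
|---|---|---|---|
| 0.3 | −4.55 | 5.1% | 84.2% |
| 0.5 | −4.23 | 7.3% | 78.2% |
| 0.7 | −3.91 | 10.3% | 72.4% |
| 0.85 | −3.68 | 13.3% | 67.3% |

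Selective loss alike in both arms gives −4.98 and −4.99 (ρ = 0.3 and 0.85), with error 2.5% and 2.2%. Milder cases at ρ = 0.7 give 4.9% (worst 70%) and 5.2% (5 lost per arm).

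**4. What a repeated-measures model recovers.** In the same scenarios it gives about −5.0 with 2.6% to 3.0% false non-inferiority, and 90% to 93% power. If loss depends on the Month-12 value itself, it corrects only partly: 15.5%, 8.5% and 5.8% at ρ = 0.3, 0.7 and 0.85, against about 18% for completers.

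**5. Who has a Month-12 visit in wait-and-extend.** Start at Day 90 with a 4-week interval; a stable visit adds 2 weeks up to 8, a negative change returns to 4. This gives 208 possible paths to Day 353 or later. On nominal days, 57 have a visit on Day 353-367 (Day 360 ± 7). If the visit may also move by 7 days, 143 can. These count paths, each weighted equally, and are not shares of patients.

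**The case against.** **SAP 6.9 may supply a rule.** It refers to the last available visit and the final visit, and a reader might infer last-value carry-forward. It does not support that: the text covers descriptive tables and a within-arm first-to-final test. SAP 6.14.1 uses Month 12 and does not refer to it.

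**Loss may be small.** Protocol 5.5.9 keeps patients who stop drug in the study and encourages the final assessments. This stands as a mitigating factor, but it is not an analysis rule.

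**The illustration is chosen.** No document says that loss will be selective in one arm only, and the main scenario suits the model because loss depends on a value the model sees. Both points stand. A favourable result could also be robust: at an observed difference of 0 and ρ = 0.7, with a mean half-width of 2.90, missing wait-and-extend patients would need a penalty of (5 − 2.90) × 52/10 = about 11 letters to overturn it. At an observed −1 the same sum is (4 − 2.90) × 5.2 = about 6. Only a planned analysis would show where the trial lies.

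**Month-12 timing.** From the nominal count a reader might infer that most wait-and-extend patients have no Month-12 visit, or that one negative change is enough to miss it. The documents do not support this. Four of the five single-negative-change paths plan Day 370, which the visit window lets fall on Day 363. Completion at Month 12 (Protocol 5.5.10) and the compulsory Month-12 angiography (Protocol 6 footnotes, Protocol 6.4, SAP 6.12) suggest that an assessment is intended in both arms. What remains is that no text says how it fits the extended intervals.

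**Baseline.** Visit 2 is labelled baseline, but "if all the assessments/examinations are performed during Screening/Visit 1, they should not be repeated in Baseline/Visit 2" (Protocol 6.2). This is loose wording, settled by one sentence.

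**Conclusion.** The gap is real and should be closed, because it affects the primary non-inferiority comparison and the sponsor itself expects 20% loss. The documents contain prevention and extra enrolment, but no rule for a missing Month-12 BCVA and no sensitivity analysis. That the comparison then rests on Month-12 completers is an inference, though a sound one.

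The bias is conditional and can go either way. It would be wrong to conclude that the plan favours wait-and-extend, or that bias is certain. Under the stated assumptions it is about 0.5 to 1.3 letters, with false non-inferiority of about 5% to 13% or power of about 84% to 67%. Milder loss gives about 5%, and loss alike in both arms gives none. The error rates also rest on a decision rule that the SAP does not state. The illustration takes 104 as randomised (Protocol 9.7, SAP 5.1); Protocol 4 and SAP 5 give 104 as screened and 86 as randomised, which needs separate reconciliation.

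**What to change.** 1. **Population.** Analyse efficacy in all randomised patients as randomised, including BCVA measured after stopping study drug. Keep the Safety population for safety.
2. **Primary estimate.** Use the Month-12 contrast (wait-and-extend minus labelled, with 95% interval) from a mixed model for repeated measures on study-eye BCVA. Terms: baseline BCVA (last value before the first injection), arm, window and arm-by-window. Prespecify non-overlapping windows, for example around Months 1, 3, 6, 9 and 12, a rule for two visits in one window, the covariance structure with a fallback, and the degrees-of-freedom method. State which window takes a completion visit outside Day 353-367.
3. **Sensitivity.** Plan one tipping-point analysis: lower the imputed Month-12 BCVA of missing wait-and-extend patients until the conclusion changes, and report that penalty. It is needed because the model corrects only partly if loss depends on the Month-12 value itself.
4. **Timing.** Reconcile Protocol 5.2, 5.5.10, 6 (table and footnotes) and 6.4 on how the Month-12 assessment fits the wait-and-extend intervals. Whatever is settled, the SAP should say how that assessment counts towards the number-of-visits endpoint.

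**Cost.** Protocol and SAP wording and modest programming; BCVA is already scheduled at every visit. The primary model brings a missing-at-random assumption, and the results may be less favourable than those from completers.
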